2 INTRODUCTION

2.1 STUDY RATIONALE

ADHD is one of the most common pediatric psychiatric conditions and best practice for its treatment includes both pharmacological (usually psychostimulants – methylphenidate or amphetamine) and non-pharmacological (behavioral or cognitive-behavioral therapy). These treatment modalities have demonstrated incontrovertible short-term benefits across core symptoms of ADHD and associated impairments. However, there are limitations to current best practices for the treatment of ADHD.

Pharmacological interventions are accompanied by adverse events in many children, do not normalize functioning, and adherence rates over time are generally low. The latter aspect is likely because longer-term benefits of medication for ADHD are modest. Longitudinal studies have shown that acute improvements in ADHD symptoms and functioning are not maintained beyond 24-36 months.

With respect to non-pharmacological interventions, access to such services can be a challenge for several reasons, including the number of qualified providers and coverage by third-party payers.

Given these limitations to current standards of care, there is a strong need for the development of additional interventions for ADHD that can be easily and widely disseminated. Given the central role of attention and other aspects of cognition in the pathophysiology of ADHD, interventions that specifically target these constructs in safe and effective ways are particularly needed.

While a previous pivotal (FDA Registration) trial demonstrated efficacy and safety of AKL-T01 in children not currently taking psychostimulants, much is still unknown about the effect of AKL-T01 on symptoms and impairments of children currently treated with psychostimulants. Specifically, it is unknown whether AKL-T01 offers additional clinical benefit to patients who are treated with stimulants. In addition, little is known about the sustained effects of AKL-T01 in either stimulant-treated or untreated children. Examining the durability of treatment effects of AKL-T01 will be important for patients and their families, providers, and payers. Relatedly, it is not currently known how additional treatment cycles with AKL-T01 following the initial 28-day regimen will affect outcomes. Addressing this issue will also be critically important for developing long-term treatment plans with AKL-T01 in pediatric populations.

The current study seeks to address these unanswered questions. Specifically, this study aims to determine the effect of AKL-T01 in children with ADHD who are currently treated – but inadequately managed – with psychostimulants. Participants will receive AKL-T01 for approximately 25-30 minutes per day, 5 days per week, over a 4-week treatment period, for two treatment periods separated by a one-month break. Change in Baseline on the IRS (Clinician Report) will serve as the primary outcome variable and will allow for a determination of whether AKL-T01 significantly improves impairments in pediatric patients with ADHD. Secondary measures will include measures of ADHD symptoms, objective measures of attention, and measures of participant and parent/caregiver experience and preference.

2.2 BACKGROUND

Front-line treatment for ADHD includes the use of stimulant medications, which is effective in reducing core symptoms of the disorder but are associated with well-documented side effects. In addition, there is recent evidence that pharmacological treatment may not show optimal benefits in some cognitive domains (Biederman, et al 2015). Computerized cognitive training programs have shown some promise in improving working memory and attention in ADHD populations (Klingberg, et al 2005). Further research is needed to validate the effectiveness of currently available computerized cognitive interventions as well as consumer-grade gamified therapies that are still being developed.

This protocol will evaluate the effects of a novel, highly-immersive, videogame-based intervention for ADHD as adjunctive treatment to stimulants while also providing a mobile app to track symptoms. AKL-T01 was derived from a comparable cognitive training program shown to have robust effects on working memory, attention, and related constructs in older adults (Anguera, et al 2013). AKL-T01 is deployed on mobile devices (i.e. tablets) and incorporates adaptive, simultaneous cognitive tasks in a consumer-grade action videogame-like platform with high-quality graphics and reward mechanisms.

Novel, cost-effective, non-pharmacological interventions for ADHD which are easy to implement and disseminate could be helpful for many participants given the limitations of other approved interventions.

Most relevant to the current protocol is the recently-completed pivotal study STARS-ADHD; a multi-center, randomized, double-blind, active-controlled study comparing AKL-T01 treatment to the use of EVO Words active control in 348 pediatric participants (180 participants were randomized into AKL-T01, and 168 into the control group EVO Words) ages 8-12 diagnosed with ADHD. The study was conducted across 20 sites that were geographically distributed nationwide. Study participants must either have been (a) currently off ADHD medication or (b) currently receiving ADHD medication but inadequately managed on their current stimulant dose per investigator's judgment and willing to discontinue ADHD medication for the study.

Participants were asked to engage in AKL-T01 treatment at home for 25 minutes per day, 5 days per week, for 4 weeks. Participants were assessed using the TOVA, ADHD-RS, IRS, and BRIEF.

The study successfully demonstrated a statistically significant improvement ($p=0.006$) between AKL-T01 and EVO Words on the primary endpoint (TOVA-API change from Baseline to Post-Treatment) (STARS-ADHD, in progress). This improvement in TOVA-API score based upon treatment is indicative of a clinically meaningful benefit for AKL-T01 participants. This conclusion is supported by the results of the study secondary endpoints, which all consistently trended towards improvement. In this study, AKL-T01 demonstrated a favorable safety profile, with no serious adverse events observed.

2.3 RISK/BENEFIT ASSESSMENT

2.3.1 KNOWN POTENTIAL RISKS

The risks to a participant taking part in this study are minimal. The study involves completing some computerized tests, game-based digital therapies, and answering some questions. It is possible that the participant could become frustrated by some of the tasks. The participant could become fatigued by the computer tests or therapeutic play. If the participant becomes frustrated or fatigued, they may stop at any time. There are no other risks to taking part in this study of which we are aware.

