8.3.3 PREVIOUSLY KNOWN ADVERSE DEVICE EFFECTS

AKL-T01 (instructions for use)....The expectedness of an ADE shall be determined according to the specified reference document containing safety information (e.g., Instructions for Use) and the expected ADEs listed below. Any ADE that is not identified in nature, severity, or specificity in the current investigational product reference documents is considered unanticipated.

Adverse Device Effects expected for this device are as follows:

- Dizziness
- Nausea
- Headache
- Decreased frustration tolerance
- Emotional reaction

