8.3.4.3 EXPECTEDNESS

The DCRI Safety Medical Monitor will be responsible for determining whether an ADE is expected or unexpected for events meeting serious criteria. An ADE will be considered unexpected if the nature, severity, or frequency of the event is not consistent with the risk information previously described for the study treatment.

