10 SUPPORTING DOCUMENTATION AND OPERATIONAL CONSIDERATIONS

10.1 REGULATORY, ETHICAL, AND STUDY OVERSIGHT CONSIDERATIONS

10.1.1 INFORMED CONSENT PROCESS

10.1.1.1 CONSENT/ASSENT AND OTHER INFORMATIONAL DOCUMENTS PROVIDED TO PARTICIPANTS

Consent forms describing in detail the study treatment, study procedures, and risks are given to the participant, and written documentation of informed consent is required before starting treatment/administering study treatment.

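### Section 2.3.1 denies any known risk beyond frustration and fatigue, yet section 8.3.3 lists at least three further expected device effects, and sections 8.3.4.3 and 8.4.1 do not tie expectedness to that list

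*Combined protocol and SAP*

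**What the plan says.** Section 2.3.1 (Known Potential Risks) describes the risks as minimal and names two. On frustration: "It is possible that the participant could become frustrated by some of the tasks". On fatigue: "The participant could become fatigued by the computer tests or therapeutic play". It then states: "There are no other risks to taking part in this study of which we are aware".

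Section 8.3.3 (Previously Known Adverse Device Effects) introduces a list with the words "Adverse Device Effects expected for this device are as follows". The items are dizziness, nausea, headache, "Decreased frustration tolerance" and "Emotional reaction". The same section says that expectedness is determined from the safety reference document, with the Instructions for Use as the example, together with this list.

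Three other clauses depend on what counts as known:

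- Section 8.3.2 defines an unanticipated adverse device effect (UADE). It points by number to 8.3.3 as the list of anticipated events and also requires that the event be serious.
- Section 8.3.4.3 gives the medical monitor the expectedness decision for serious events. An event is unexpected "if the nature, severity, or frequency of the event is not consistent with the risk information previously described" for the study treatment. No section or document is named.
- Section 8.4.1 defines unanticipated problems. It judges unexpectedness against protocol-related documents generally, with the approved protocol and the consent document as examples.

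On what families receive, section 10.1.1.1 says: "Consent forms describing in detail the study treatment, study procedures, and risks are given to the participant".

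**The concern.** A sponsor cannot both expect an effect of its device and be unaware of it as a risk. Section 2.3.1 is the protocol's risk statement, and under the Statement of Compliance the protocol goes to the IRB for approval. In a trial of children aged 8 to 14, that statement should agree with the list of effects the sponsor already expects.

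Two things could follow. First, if the consent and assent forms took their risk text from 2.3.1, families would not be told about dizziness, nausea or headache. Second, where a clause asks whether an event was previously described without saying where to look, 2.3.1 and 8.3.3 give different answers for some events.

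**Working it through.** No figure in the plan is at issue, so the check compares the two lists item by item and then reads each expectedness clause.

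**Step 1. Compare the lists.**

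| Effect | In 2.3.1 | In 8.3.3 |
|---|---|---|
| Frustration / decreased frustration tolerance | yes | yes |
| Fatigue | yes | no |
| Dizziness | no | yes |
| Nausea | no | yes |
| Headache | no | yes |
| Emotional reaction | not named | yes |

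Section 8.3.3 has 5 items. Dizziness, nausea and headache have no counterpart in 2.3.1, so at least 3 of 5 are missing. If emotional reaction is treated as distinct from frustration, 4 of 5 are missing. In reverse, 2.3.1 has 2 items, and 1 of them (fatigue) is not in 8.3.3.

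**Step 2. Read the closing sentence against the list.** The sentence in 2.3.1 allows no exceptions. One expected effect outside 2.3.1 would contradict it, and there are at least three. The contradiction needs no outside source and does not depend on how emotional reaction is classified.

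**Step 3. Find where the mismatch can affect a classification.**

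| Clause | Applies to | Reference named | Criteria |
|---|---|---|---|
| 8.3.2 | UADEs | section 8.3.3 | absence from that list, relatedness per the sponsor, seriousness |
| 8.3.3 | device effects | reference document plus its own list | nature, severity, specificity |
| 8.3.4.3 | serious device effects | none | nature, severity, frequency |
| 8.4.1 | unanticipated problems | protocol-related documents generally | nature, severity, frequency |

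In the first two rows, 2.3.1 plays no part. In the last two it can, because it is risk information that stands in the protocol. Those two clauses also test frequency where 8.3.3 tests specificity. The list in 8.3.3 gives no frequencies, so within the protocol there is nothing to compare a frequency with.

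**Step 4. Take one event through the clauses.** Fatigue is not in the 8.3.3 list. Under that section it would be unanticipated only if the Instructions for Use, which were not available for review, also omit it. Under 8.4.1 the whole protocol counts, 2.3.1 included, so fatigue is a described risk. Under 8.3.4.3 a serious fatigue event could be read either way, because no source is named. Nausea, headache and dizziness have a clear answer under 8.3.3: they are listed.

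**The case against.** The case on the other side is that this is a mismatch of text with little consequence, and much of that case stands.

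- *Families.* A reader might infer that families are told too little, and that this touches all 203 of them. The documents do not show that. The consent form was not available for review, section 10.1.1.1 says that consent forms describe the risks in detail, and nothing in the protocol says the consent text is taken from 2.3.1. The point can be raised only as a check.
- *Expectedness in general.* A reader might infer that every expectedness decision depends on which list is read, or that such decisions cannot be reproduced. Sections 8.3.2 and 8.3.3 rule out the general form, since both name 8.3.3. The ambiguity is limited to 8.3.4.3 and 8.4.1. In 8.3.4.3, moreover, a serious event may exceed in severity anything that either list implies.
- *Under-reporting.* A reader might infer that parents who have not been warned will not report headaches or nausea. Section 8.3.5 has the investigator ask about device effects at each visit and has them documented whatever their relationship to treatment. The Schedule of Activities collects adverse events from baseline through Day 84. Under-ascertainment is not shown, and the documents give no frequencies from which to size it.
- *Fatigue.* Section 2.3.1 attributes fatigue to the computer tests as well as to play, so it need not be a device effect. Its status also depends on the Instructions for Use.
- *Risk/benefit.* The evidence that 2.3.3 gives for its favorable conclusion is the absence of serious adverse events. Completing the risk list would not remove that evidence.

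None of this reaches the contradiction itself. The closing sentence of 2.3.1 remains incompatible with 8.3.3.

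**Conclusion.** The contradiction is established from the protocol alone. Section 2.3.1 denies known risks that 8.3.3 lists as expected: 3 of 5 items at least, 4 of 5 if emotional reaction is counted separately. One of the two risks in 2.3.1 has no place in 8.3.3. The consequence for expectedness is narrow: 8.3.4.3 (serious events, no source named) and 8.4.1 (the protocol and consent document generally), both with criteria that differ from those in 8.3.3.

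Two parts are conditional. That families may be told too little assumes the consent and assent text follows 2.3.1. That fatigue would be unanticipated under 8.3.3 assumes the Instructions for Use also omit it. Neither document could be checked.

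The correction should be made because it concerns a false safety statement in a pediatric protocol and costs little. It does not touch the endpoints, the sample size or the efficacy analysis.

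**What to change.** 1. Delete the closing sentence of 2.3.1 and carry the five effects from 8.3.3 into that section.
2. State whether fatigue is regarded as an expected device effect. If so, add it to 8.3.3; if not, say so in 2.3.1.
3. Have 8.3.4.3 and 8.4.1 cite 8.3.3 plus the Instructions for Use as the single reference for device effects, and use the same criteria in all three sections. If frequency stays as a criterion, say where the reference frequencies are found.
4. Check the risk text of the consent and assent forms against the reconciled list, and update the forms if they follow 2.3.1.

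The cost is protocol wording, IRB review of the change, a slightly less favorable risk statement and, if step 4 finds a gap, a consent update. No study procedure changes.

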2.3.2 KNOWN POTENTIAL BENEFITS

Based on preliminary data obtained in several studies including a recent registration trial in children with ADHD, the potential benefit of the AKL-T01 game-based treatment for this population is to increase attentional functioning. Given the central role of attention in the pathophysiology of ADHD, this benefit is substantial.

2.3.3 ASSESSMENT OF POTENTIAL RISKS AND BENEFITS

To date, there have been no serious adverse events reported across several studies with the device. The risk/benefit ratio for use is favorable.

3 OBJECTIVES AND ENDPOINTS

OBJECTIVES	ENDPOINTS	JUSTIFICATION FOR ENDPOINTS
Primary		

Cohort 1: To understand the synergistic impairment effects when combining AKL-T01 (with AKL-X01 symptom tracking) as adjunctive treatment to stimulant medication.
 
Cohort 2: To understand the impairment effects of AKL-T01 (with AKL-X01 symptom tracking) treatment in participants not recently on stimulant medication.
	
Cohort 1, Cohort 2:
 
 1) Overall change in clinician-reported Impairment Rating Scale (IRS) "Overall severity of child's problem in functioning and overall need for treatment" score from baseline to Day 28. 	
Cohort 1: The overall change in Impairment Rating Scale (Clinician Report) from baseline to Day 28, in participants on stimulant medication, will demonstrate the overall effect that AKL-T01 has on ADHD related impairments when administered in addition to stimulant medication. The IRS score measures the effects on individualized functional impairments.
 
Cohort 2: The overall change in IRS (Clinician Report) from baseline to Day 28, in participants not currently on stimulant medication, will demonstrate the overall effect that AKL-T01 has on ADHD related impairments when administered without stimulant medication. The IRS score measures the effects on individualized functional impairments.

Secondary		
To understand symptom and attentional effects of AKL-T01 (with AKL-X01 symptom tracking) in all participants (both Cohort 1 and Cohort 2).	
Cohort 1, Cohort 2:
 
 1) Overall change in ADHD-Rating Scale (ADHD-RS) total component score from baseline to Day 28. 2) Clinical Global Impression-Improvement (CGI-I) score at Day 28. 3) Overall change in Test of Variable Attention-Version 9 (TOVA) attention composite score (ACS) and certain constituent scores, from baseline to Day 28 (the specific constituent scores will be described in the SAP). 	Measuring and analyzing the overall change in ADHD-Rating Scale and Test of Variable Attention-Version 9 from baseline to Day 28, and the Clinical Global Impression – Improvement score at Day 28, will assist with assessing the impact of AKL-T01 on ADHD symptoms within the short-term following treatment administration.

OBJECTIVES	ENDPOINTS	JUSTIFICATION FOR ENDPOINTS
Exploratory/Descriptive Sustained benefits, through reduction of ADHD impairment and symptoms, following 1-Month of AKL-T01 treatment (with AKL-X01 symptom tracking) (both Cohort 1 and Cohort 2).	
Exploratory (Cohort 1, Cohort 2):
 
 1) Overall change in clinician-reported IRS “Overall severity of child’s problem in functioning and overall need for treatment” score from baseline to Day 56 and from baseline to Day 84. 2) Overall change in ADHD-RS total component score from baseline to Day 56 and from baseline to Day 84. 3) CGI-I score at Day 56 and at Day 84. 4) Overall improvement in TOVA ACS and certain constituent scores, from baseline to Day 56 and from baseline to Day 84. 5) Overall change in Test of Silent Reading Efficiency and Comprehension (ToSREC) from baseline to Day 28 and from baseline to Day 84, using the appropriate ToSREC form. 6) Overall change in Mathematics Fluency and Calculation Tests (MFaCTs) from baseline to Day 28 and from baseline to Day 84, using the appropriate MFaCTs form. 
Descriptive (Cohort 1, Cohort 2):
 
 1) AKL-X01 usage, as compared to the expected usage of 5 days per week. 2) Participant/Caregiver experience and preference questionnaires. 3) Participant demographics. 4) Reported adverse events. 5) Change in participant’s medications. 6) Constituent measures of the IRS (individual questions), ADHD-RS (sub-scales and individual questions), and TOVA. 	
Measuring the overall change from baseline to Day 84 will examine the sustained effects of AKL-T01 on ADHD symptoms after 1-Month of treatment and 1-Month break, and a follow-on month of treatment in both Cohorts 1 and 2 (analyzed individually).
 
Measuring the overall change from baseline to Day 56 will examine the sustained effects of AKL-T01 on ADHD symptoms after 1-Month of treatment and 1-Month break in both Cohorts 1 and 2 (analyzed individually).

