4 STUDY DESIGN

4.1 OVERALL DESIGN

This study is a multi-center, open label trial to determine the effect of AKL-T01 treatment (with AKL-X01 mobile app-based symptom tracking) on ADHD symptoms and impairments in children currently on or off stimulant.

Two hundred and three participants (203) at multiple sites will be enrolled into 2 cohorts. 130 participants will be recruited into cohort 1 and 73 participants will be recruited into cohort 2.

Cohort 1 will have been stable** on stimulant(s) for at least 30 days before baseline. At screening (at least 7 and up to 30 days before baseline), participant caregivers will be instructed to download AKL-X01 on to their smartphone. Caregivers will use AKL-X01 for tracking participants' symptoms and behaviors beginning between days -30 and -7, through day 84. During Treatment Phase 1, Days 1 through 28, participants will continue receiving stimulant and will also receive AKL-T01 treatment. During the 1-month treatment pause, Days 29 through 56, participants will continue receiving stimulant but will discontinue AKL-T01. During Treatment Phase 2, Days 57 through 84, participants will continue receiving stimulant and will also receive AKL-T01 treatment.

****Note:** Medication stability is defined as:

- Moderate response on stimulant, but still room for improvement
- Dose unchanged within past 30 days, but other doses have been tried previously without improvement
- Currently taking stimulant, but parent and/or caregiver wishes not to increase dosage for any reason
- Taking consistent stimulant dose on weekdays, but not on weekends

The hypothesis for Cohort 1 is that children receiving stimulant plus AKL-T01 treatment will improve in ADHD symptoms and impairments from Day 0 to Day 28.

Cohort 2 will have been stable without any stimulant for ≥ 30 days before baseline. At screening (at least 7 and up to 30 days before baseline), participant caregivers will be instructed to download AKL-X01 on to their smartphone. Caregivers will use AKL-X01 for tracking participant symptoms and behaviors beginning between days -30 and -7, through day 84. During Treatment Phase 1, Days 1 through 28, participants will receive AKL-T01 treatment. During the 1-month treatment pause, Days 29 through 56, participants will discontinue AKL-T01. During Treatment Phase 2, Days 57 through 84, participants will receive AKL-T01 treatment.

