9 STATISTICAL CONSIDERATIONS

This section provides a brief overview of the statistical analyses, both quantitative and qualitative in nature that will be used during this study. In addition to what follows in this section, further details will be provided in a separate statistical analysis plan (SAP).

The primary objectives of this study are to (1) understand the synergistic impairment effects when combining AKL-T01 (with app-based symptom tracking, AKL-X01) as adjunctive treatment to stimulant medication, and (2) understand the impairment effects of AKL-T01 (with app-based symptom tracking, AKL-X01) treatment in participants not recently on stimulant medication. Within both the medicated and non-medicated cohorts, a change in Impairment Rating Scale (IRS) (Clinician Report) from baseline to Day 28 will demonstrate the overall effect that AKL-T01 treatment has on ADHD symptoms.

The secondary objective of this study is to understand the symptom and attentional effects of AKL-T01 (with app-based symptom tracking AKL-X01) treatment in all participants. There is an additional exploratory objective which focuses specifically on sustained benefits, through reduction of ADHD symptoms and impairment, experienced by participants following (a) 1-month of treatment with AKL-T01, and (b) an additional 4 weeks of AKL-T01 treatment.

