9.1 STATISTICAL HYPOTHESES

The aim of the primary objective is to demonstrate a statistically significant difference on mean change in IRS “Overall severity of child’s problem in functioning and overall need for treatment” score, defined for each participant as the score measured on Day 28 minus the score measured at the baseline visit. In both the medicated and non-medicated cohorts, the statistical significance of the primary efficacy analysis will be assessed using a 2-sided paired *t*-test evaluated at the 95% level of confidence. The formulation of the null (H_0) and alternative (H_a) hypotheses are stated below, where μ_d refers to the true mean difference:

- $H_0: \mu_d = 0$
- $H_a: \mu_d \neq 0$.

If, within a particular cohort, the upper bound of the 95% confidence interval around the sample difference is smaller than 0, we will have sufficient evidence to reject H_0 and conclude that AKL-T01 plus Fengo improves ADHD symptoms in that cohort.

If the set of sample differences is non-normal, defined here as skewness larger than 1.5 in magnitude, the efficacy analysis will proceed as a non-parametric Wilcoxon signed rank test. Significance will be determined by evaluating the *W*-statistic at the 95% level of confidence.

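### The Cohort 1 objective claims synergy and the plan prespecifies a causal conclusion, but the only primary test is within-cohort change from baseline with no concurrent control

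*Combined protocol and SAP*

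**What the plan says.** The Cohort 1 primary objective in Section 3 is "To understand the synergistic impairment effects when combining AKL-T01 (with AKL-X01 symptom tracking) as adjunctive treatment to stimulant medication". The synopsis (Section 1.1) says the same in substance, and Section 9 repeats the aim to "understand the synergistic impairment effects when combining AKL-T01" with stimulant. Section 2.1 gives the motive: "it is unknown whether AKL-T01 offers additional clinical benefit to patients who are treated with stimulants".

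The justification column of Section 3 says that the Cohort 1 change from baseline to Day 28 "will demonstrate the overall effect that AKL-T01 has on ADHD related impairments when administered in addition to stimulant medication". It makes a parallel statement for Cohort 2, and Section 9 makes the claim for both cohorts together. Section 2.1 adds that the endpoint will settle whether AKL-T01 significantly improves impairment.

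What is tested is narrower. Section 4.1 describes the study: "This study is a multi-center, open label trial to determine the effect of AKL-T01 treatment". Its Cohort 1 hypothesis is that "children receiving stimulant plus AKL-T01 treatment will improve in ADHD symptoms and impairments from Day 0 to Day 28". Under Section 9.1, "the statistical significance of the primary efficacy analysis will be assessed using a 2-sided paired" t-test in each cohort, with a signed rank test if the differences are skewed. If the upper 95% bound is below zero, Section 9.1 directs the conclusion that AKL-T01 plus Fengo improves ADHD symptoms in that cohort. Sections 9.4.1 and 9.4.2 keep the comparisons within cohort and leave covariates out of the primary analysis.

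**The concern.** Synergy is an interaction: the effect of AKL-T01 with stimulant set against its effect without. Added benefit over stimulant is a smaller claim, but it still needs a reference for what children on stimulant alone would have done over the same 28 days. The primary analysis contains neither contrast.

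A paired test against zero collects everything that moves the score between two visits. The protocol supplies several sources besides the device. Treatment is open label and the endpoint is clinician-rated; Section 6.2 shields raters only from compliance reports. Children enter on a Parent IRS of at least 3 at Screening and on CGI-S. Section 1.3 schedules CGI-S at Baseline, the visit of the first clinician IRS, so regression to the mean is possible. With no earlier clinician IRS, no pre-treatment trend can be estimated.

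At stake is what a positive result may be called. As written, the plan would report it as an AKL-T01 effect, against an objective of synergy.

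**Working it through.** **Inputs.** From Section 9.2: SD of change 1, 90% power, effect sizes 0.30 (Cohort 1) and 0.40 (Cohort 2), effective n of 117 and 66, 10% dropout. From Section 9.1: two-sided 5% test, success if the upper 95% bound is below zero. The background improvement m is assumed; the documents give no IRS change for an untreated or control group.

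**1. The plan's own sample size.** n = ((1.960 + 1.282)/d)², and (1.960 + 1.282)² ≈ 10.507.
- d = 0.30: 10.507/0.09 = 116.7, so 117.
- d = 0.40: 10.507/0.16 = 65.7, so 66.
- Dropout: 117/0.9 = 130. 66/0.9 = 73.3, which rounds up to 74 against the stated 73; this does not affect the point.

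The exact t calculation gives 119 and 68, with power 89.6% at 117 and 89.3% at 66. The figures reproduce. They size a one-sample test against zero change, not a comparison with stimulant alone.

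**2. Chance of success when the device does nothing.** Let the true device effect be zero and the mean background improvement be m. The chance of meeting the success rule is the improvement tail of a non-central t with n − 1 degrees of freedom and non-centrality m√n/SD (√117 = 10.82, √66 = 8.12).

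| m (assumed) | Cohort 1, n = 117: non-centrality | Chance of success | Cohort 2, n = 66: non-centrality | Chance of success |
|---|---|---|---|---|
| 0 | 0 | 2.5% | 0 | 2.5% |
| 0.10 | 1.08 | 19% | 0.81 | 12% |
| 0.20 | 2.16 | 57% | 1.62 | 36% |
| 0.30 | 3.25 | 90% | 2.44 | 67% |
| 0.40 | 4.33 | 99% | 3.25 | 89% |

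**3. What the stated objective would need** (SD 1, two-sided 5%, 90% power).
- Concurrent stimulant-alone arm, net difference 0.30: 2 × 10.507/0.09 = 233.5, so 234 per arm, 468 evaluable, and 468/0.9 = 520 enrolled.
- Synergy as a 2×2 interaction of 0.30: 4 × 10.507/0.09 = 467 per cell, 4 × 467 = 1,868 evaluable.

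**4. Would contrasting the two existing cohorts help?** The standard error is √(1/117 + 1/66) = 0.154. The plan's planning effects differ by 0.40 − 0.30 = 0.10, with the smaller change on stimulant. Power for a gap of 0.10 is about 9.5%. More basically, the cohorts are not randomised and neither has an untreated reference, so a gap between them would not isolate synergy.

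**The case against.** The best defence is that this is a declared open-label follow-up after a randomised pivotal trial. The single-group design is chosen and disclosed, Section 6.2 has rater safeguards, and the hypothesis in Section 4.1 can be answered. That stands: the design need not change. It does not rescue the objective or the conclusion rule, which claim more than the hypothesis does.

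A reader might infer that the trial has no stimulant-only data at all. The documents do not support this. Cohort 1 children are on stimulant without AKL-T01 at Day 0, after at least 30 days on it, and again through Days 29 to 56, with a clinician IRS at Day 56. This is some information. But Day 0 cannot remove time, expectancy or regression, and Day 56 comes after the primary endpoint, is open to carry-over, and is only summarised descriptively (Section 9.4.9). What is missing is a concurrent stimulant-alone control.

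The false-success figures are conditional. The 90% at 0.30 and 89% at 0.40 are the design power under another name. Regression is attenuated because the IRS entry threshold uses the parent form at Screening while the endpoint is the clinician form from Baseline. Section 4.2 also reports no significant pre-post change in the pivotal control group (p = 0.67). That result is for a TOVA index in a blinded trial, so it says little about an open-label clinician rating.

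It is also tempting to subtract the pivotal control arm's IRS change as a benchmark, since Section 2.2 says "Participants were assessed using the TOVA, ADHD-RS, IRS, and BRIEF". The documents do not support this use. That trial was double-blind in children off ADHD medication, so the subtraction would not address Cohort 1 or remove open-label expectancy. Section 2.2 also does not state the IRS version or how many of the 168 control children had a Day 28 IRS.

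Finally, the protocol defers detail to a separate SAP, so the absence of an interaction or between-cohort test is a statement about the available text. The primary analysis itself is fully specified there.

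**Conclusion.** The point holds as a mismatch between claim and analysis. The plan can show whether mean clinician-rated IRS changed from baseline to Day 28 in each cohort. It cannot show synergy, and it cannot attribute the change to AKL-T01 over ongoing stimulant. Because Section 9.1 prescribes the causal conclusion, this is more than loose wording in an objective.

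The size depends on background change, which the documents do not give. At SD 1 and the planned evaluable numbers, a background improvement of 0.10 to 0.30 gives an inert device a 19% to 90% chance of success in Cohort 1. In Cohort 2, 0.10 to 0.40 gives 12% to 89%. The nominal rate is 2.5% in each. These figures do not show that background change of this size will occur, or that AKL-T01 is ineffective; they show that the success rule cannot tell the two explanations apart.

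**What to change.** Change the wording in five places:

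- **Synopsis (1.1), Section 3 and Section 9, Cohort 1 objective:** delete *synergistic*. Restate as: *to estimate the 28-day change in clinician-rated impairment while AKL-T01 is added to ongoing stimulant*.
- **Section 3 (justification column) and Section 9, both cohorts:** replace the claim that the change demonstrates the AKL-T01 effect with *will describe the change during AKL-T01 use*.
- **Section 9.1, conclusion rule:** replace with *mean IRS score improved from baseline to Day 28 during AKL-T01 plus Fengo use in that cohort*, with no attribution to AKL-T01.
- **Section 2.1:** bring the sentence on what the primary outcome will determine into line.

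Do not add a between-cohort test or a pivotal-trial control benchmark as a substitute for a control group.

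The tests and the sample size (117 and 66 evaluable, 130 + 73 enrolled) are unchanged. The cost is a weaker stated claim. If the sponsor wants the comparative claim, it needs a concurrent control and a new sample size, of the order shown in step 3 of the working.
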